5.4.9 Vaccine Dose #3

Note: this visit must be conducted no earlier than 16 weeks after Vaccine Dose #2 and no later than Week 32

5.4.9.1 Sexually active female participants of childbearing potential will be instructed to use contraception beginning with first vaccine dose and continuing until at least 4 weeks after all 3 vaccine doses have been administered. Participants will be queried prior to each dose to determine if there is a possibility of pregnancy. If there is any possibility of pregnancy, a pregnancy test (urine or blood as per local institutional preference and procedures) will be obtained prior to vaccine administration and if positive, the vaccine will be withheld and the participant withdrawn from receiving further vaccine on the study. The vaccine will not be administered to sexually active females who refuse contraception.

5.4.9.2 Targeted review of systems/ screening for acute illness and medication review will be performed. Vaccine administration must be rescheduled if any of the following are

present:

- Serious active infection (afebrile upper respiratory infection is not considered a serious infection)
- Fever $\geq 100^{\circ}\text{F}$ or $\geq 37.8^{\circ}\text{C}$ (oral) within 24 hours prior to the visit
- Receipt of any vaccines within 2-4 weeks prior to visit (as per Section 5.4.5)
- If acute or chronic medical or surgical conditions or contraindications not described above are present, the site investigator should consult with the coordinating center PI to obtain clearance to administer the vaccine

Vaccine Visit Form (Appendix 8) will be completed and submitted.

The most recent version of the Gardasil® (for patients enrolled on or before 3-1-16) or Gardasil®9 (for patients enrolled after 3-1-16) Vaccine Information Statement (VIS), as posted at www.cdc.gov/vaccines/pubs/vis/default.htm (sample in Appendix 13), will be given to the patient/parent.

- 5.4.9.3 HPV Vaccine Dose #3 (Gardasil® for patients enrolled on or before 3-1-16; Gardasil®9 for patients enrolled after 3-1-16) will be administered (0.5 ml IM per instructions in Section 5.4.3). Syncope has been reported following vaccine administration and may result in falling with injury; participant will be observed for 30 minutes following vaccine administration to assess for any adverse reactions. As with all vaccines, a solution of 1:1000 epinephrine will be available for injection in the event an anaphylactic reaction were to occur.

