5.4.12 Premature Study Discontinuation Visit

Administration of the study vaccine must stop permanently and a Premature Study Discontinuation Visit scheduled if any of the following occur:

- A confirmed Grade ≥ 3 toxicity that is deemed possibly, probably, or definitely vaccine-related and not resolved to \leq Grade 1 by the next due date for vaccine administration
- A Grade ≥ 3 toxicity recurs after the next administration of the study vaccine
- A Grade 4 life-threatening toxicity whose relationship to the vaccine is possibly, probably, or definitely related
- The investigator determines that receipt of additional study vaccines would be detrimental to the participant's health or well-being
- The participant becomes pregnant
- The participant withdraws consent
- The participant fails to comply with study requirements so as to cause harm to herself/himself or seriously interfere with the validity of the study results
- The subject is unable to continue participation due to circumstances preventing completion of study procedures
- The study is stopped by a government agency, such as the National Institutes of Health (NIH)
- The study is stopped for other administrative reasons

Participants who are to be permanently discontinued from the study will complete a final premature study discontinuation visit before going off study, at which time the following data will be collected:

5.4.12.1 The following blood specimens will be drawn:

- Anti-HPV 4cLIA for patients enrolled on or before 3-1-16 or 9cLIA for patients enrolled after 3-1-16: 10 ml whole blood in non-SST red top tube

Specimens will be processed and shipped to the coordinating center according to the instructions in Section 5.4.6. and Appendix 11.

5.4.12.2 Premature Study Discontinuation Form (Appendix 10) will be completed and submitted.

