6.2 Potential Risks

Aim 1 (Survey): It is possible that some participants may be uncomfortable answering questions regarding their sexual history and activity; however, these questions are considered part of standard adolescent/young adult health care. Nevertheless, participants will be informed that if they do not want to answer any questions for any reason, they may skip those questions.

Aim 2 (Vaccine Evaluation): The primary risk associated with Aim 2 are the risks associated with administration of the HPV vaccine, which is believed to be safe when administered in the general population, but which has not been studied in cancer survivors. Common side effects reported in the general population have included skin redness, pain, swelling, and/or muscle soreness at the injection site. Syncope has been reported following vaccine administration and may result in falling with injury; participants will therefore be observed for 30 minutes in the clinic following vaccine administration. Some patients may experience mild to moderate fever, chills, nausea, fatigue, or headache following the vaccine. These symptoms are usually transient and resolve without intervention. Although rare, serious side effects can occur and may include rash, urticaria, dyspnea, stridor, wheezing, edema of the face, lips, or throat, pruritis, seizures, tachycardia, hypotension, and shock, or other side effects that are currently unknown in this population. As with all vaccines, a solution of 1:1000 epinephrine will be available for injection should an anaphylactic reaction occur. Since the HPV vaccine has not been tested in cancer survivors, severity of side effects could potentially be increased in this patient population and side effects that are currently unknown could potentially occur. Additionally, the drawing of blood specimens may cause local discomfort, bleeding, or bruising; rarely a small clot or infection can occur at the site of the venipuncture.

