1. HPV antibody titers (Anti-HPV 4cLIA [for patients enrolled on or before 3-1-16] or 9cLIA [for patients enrolled after 3-1-16] [Geometric Mean Titers; Seropositivity] (Day 1, Month 7, and Month 24) [Immunogenicity]
2. Vaccine Report Card (participant/parent diary of adverse events, collected for 7 days (for patients enrolled after 3-1-16) or 14 days (for patients enrolled on or before 3-1-16) following each vaccine dose, and Adverse Events/Research-Related Problems Reporting Forms [Safety/tolerability]

7.3 **Schema – Aim 1: Survey**

Aim 1: Survey

[Protocol v3, 8/17/15: Accrual goal for Aim 1 met, enrollment to survey closed]

Requirement	Pre-Entry	Study Entry
Verification of eligibility (Protocol Section 3.1)	X	
Informed consent/assent		X
Registration		X
Medical record abstraction: - Medical Record Review Form (Appendix 1) - Intensity of Treatment Rating Scale (Appendix 2)		X
Survey completion (Appendix 3)		X

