8.2.2.3. Determine the safety/tolerability of the qHPV and 9vHPV vaccine in cancer survivors

In the IT sample, the number of vaccine-associated AE within 7 (for 9vHPV) or 14 (for qHPV) days of each dose will be compared to those reported for the age- and sex-matched general population: % of subjects with injection site AEs (e.g., pain, erythema), % of subjects with systemic AEs (e.g., fever, syncope, headache, hives, rashes, diarrhea), % of subjects with serious AEs (e.g., life-threatening, result in persistent disability or death). Overall cohort: % of subjects who discontinue vaccine related to AE. AEs will be summarized descriptively as frequencies and percentages by type (injection site, systemic, serious), by vaccine dose (i.e., #1, #2, #3), and across all vaccine doses. Chi-square and exact tests will be used for comparison depending on the rarity of events. Our smallest PP subsample of 72 young females will provide 80% power to detect a difference of 0.0485 in AE rates if true rate=0.01, and a difference of 0.1068 if the true rate=0.85. For the largest PP subsample of 82 young males, the corresponding detectable differences are 0.0415 and 0.1021. For the entire PP sample of 312, the corresponding differences are 0.0189 and 0.0534. Type I error=.05 is assumed for each comparison.

8.2.2.4. (Exploratory sub-aim): Evaluate the persistence of antibody response at 2 years post vaccine initiation and identify clinical/host factors influencing response persistence.

Outcome measure (GMT): We will calculate mean GMT and 2-sided 95% CI for HPV-16 and -18 at Month 24 following vaccine initiation for PP subjects and compare them to age-, sex-, and time-matched means in the historical healthy population.²⁸ Cancer survivors will be considered to have non-inferior persistence of antibody response to a subtype at a time point if the lower 95% confidence limit for the ratio of GMT in cancer survivors to historical healthy population is $\geq 50\%$.³⁰

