9.3.3. Toxicity Management

Any symptoms that occur will be managed according to good medical practices and clinical judgment of the site investigator. Toxicities related to the vaccine will be monitored using the *Toxicity Grading Scale for Healthy Adult and Adolescent Volunteers Enrolled in Preventive Vaccine Clinical Trials*, U.S. Department of Health and Human Services, Food and Drug Administration, Center for Biologics Evaluation and Research, September 2007 (Tables 9.3.2, 9.3.3, and 9.3.4). Toxicities will generally be considered potentially vaccine-associated if their onset occurs within 7 days after receipt of a study vaccine dose. If evaluated, the toxicity should be documented on the Adverse Events/Research-Related Problems Reporting Form (AERF) within 2 working days of the evaluation. All subjects will be followed for the reporting of toxicities for 14 days following each vaccine dose. In addition, any severe or unexplained toxicity occurring after the 14 days of follow-up brought to the attention of the investigator will be evaluated for possible vaccine-association, and documented on the AERF within 2 working days of the evaluation if found to be possibly, probably, or definitely related to the vaccine. Toxicities will not be considered vaccine-associated AEs if clearly recognized alternative etiologies are identified. Alternative explanations for clinical abnormalities must be sought prior to study vaccine discontinuation.

Therapeutic interventions that may interfere with evaluation of the safety/tolerability of the vaccine should be avoided during the indicated timeframes unless medically necessary. These include a) any live attenuated vaccine administered within 28 days of any HPV vaccine dose; b) any subunit or killed vaccines (e.g., influenza, pneumococcal, antigen injections for allergy treatment) within 14 days of any HPV vaccine dose.

General toxicity management:

- If a subject develops a persistent \geq Grade 3 clinical toxicity, the subject will not be permitted to participate in this study until the toxicity has resolved to \leq Grade 1.
- All \geq Grade 3 clinical toxicities occurring within 14 days following any vaccine dose, and their

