proposed management, must be reported to the coordinating center using the AERF within 2 business days of the site's awareness of the event, regardless of relatedness. Clinical toxicities not identified in Tables 9.3.2, 9.3.3, and 9.3.4 should be graded according to the Common Terminology Criteria for Adverse Events v4.0 (<http://safetyprofiler-ctep.nci.nih.gov/CTC/CTC.aspx>).

9.3.4. Pregnancy: Sexually active females of childbearing potential will be instructed to use contraception throughout the 6-month period when the vaccine is administered. Participants will be queried prior to each dose to determine if there is a possibility of pregnancy; if so, a pregnancy test (urine or blood as per local institutional preference) will be obtained prior to vaccine administration. If positive, the participant will be withdrawn from receiving further vaccine on the study. Any pregnancy occurring during the vaccine phase of the study (i.e., Vaccine Day 1 through 4 weeks after all 3 vaccine doses have been administered) will be reported to the study coordinating center. There are no data indicating an association of adverse pregnancy outcomes or adverse effects of the developing fetus with the vaccine. Thus, if a vaccine dose is administered during pregnancy, no intervention is indicated other than withholding further doses and reporting as specified. The patient should be followed by the participating site for pregnancy outcome data (e.g., termination, miscarriage, pre-term or full-term delivery, fetal death/stillbirth, complications, single vs multiple birth, condition of infant(s), presence of congenital anomalies, etc.), which should be reported to the study coordinating center when available. The study coordinating center will report the pregnancy, and later the pregnancy outcome (with de-identified subject information only), as follows: **gHPV vaccine recipients (patients enrolled on or before 3-1-16)**: Merck Worldwide Product Safety; [contact]. **9vHPV vaccine recipients (patients enrolled after 3-1-16)**: Gardasil^{®9} Pregnancy Registry maintained by Merck (URL: www.merckpregnancyregistries.com/gardasil9; [contact]; [contact]) and Merck Worldwide Product Safety; [contact].

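### Section 8.2.2.3 reports adverse events by type and dose but not by grade, so the severity of a transient, non-serious Grade 3 reaction is lost from the stated results unless it stops vaccination

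*Combined protocol and SAP*

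**What the plan says.** Section 7.2 makes safety/tolerability a primary Aim 2 endpoint, measured by a diary kept for 7 days (9vHPV) or 14 days (qHPV) "following each vaccine dose, and Adverse Events/Research-Related Problems Reporting Forms [Safety/tolerability". Section 6.2 warns that "severity of side effects could potentially be increased in this patient population".

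For the analysis, Section 8.2.2.3 states that "AEs will be summarized descriptively as frequencies and percentages by type (injection site, systemic, serious), by vaccine dose" and across doses. It compares the percentages with injection-site, systemic and serious AEs with the general population, and adds the percentage who discontinue vaccine because of an AE. Section 9.2 lists the same items for the monitoring committee.

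Grade is used elsewhere. Section 9.3.5 sets a 1-to-4 scale. Section 9.3.3 takes all events at or above the level in "Grade 3 clinical toxicities occurring within 14 days following any vaccine dose" and says they "must be reported to the coordinating center using the AERF within 2 business days", whether related or not. (The AERF is the adverse events reporting form.) Section 5.4.12 stops vaccination for a confirmed Grade 3 or higher "toxicity that is deemed possibly, probably, or definitely vaccine-related and not resolved to" Grade 1 or below by the next dose date. It also stops it for a Grade 3 or higher toxicity that recurs after the next dose, for a related Grade 4 toxicity, on the investigator's judgement, or when "The participant withdraws consent". Section 9.4 holds accrual after two or more cases of the same Grade 3-4 toxicity with probable attribution that last beyond 72 hours.

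**The concern.** The injection-site and systemic percentages treat each subject as yes or no. A fever of 38.2 °C (Grade 1) and one of 39.5 °C (Grade 3) each count once as a systemic AE. Redness of 3 cm (Grade 1) and redness of more than 10 cm (Grade 3) each count once as an injection-site AE. If survivors react as often as healthy people but more severely, these percentages do not move.

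The protocol names increased severity as a possible risk, and any-grade injection-site rates are already high: Section 2.4.2 gives 84.9% and 90.7% for mild to moderate events in females aged 16 to 26. When most subjects have some local reaction, how severe it was says more about tolerability than whether it occurred. As written, the result can speak to severity only through serious AEs and AE-related discontinuation.

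**Working it through.** **1. Can another stated output carry the grade?** Take a Grade 3 reaction that resolves within 72 hours and is not serious.

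| Output | Does the severity show? |
|---|---|
| Injection-site or systemic % (8.2.2.3, 9.2) | Event counted; grade not shown |
| Serious AE % (8.2.2.3; definition in 9.3.1) | No; defined by outcome, not grade |
| Expedited report to the monitoring committee (Table 9.3.1) | No; Grade 3-4 must also be serious |
| Accrual hold (9.4) | No; requires non-resolution in 72 hours |
| AE-related discontinuation % | Only if the subject stops vaccination under 5.4.12 |

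The last route closes after the third dose. Section 5.4.9 says of that visit "this visit must be conducted no earlier than 16 weeks after Vaccine Dose #2 and no later than Week 32", and no fourth dose exists to be withheld.

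**2. The plan's own safety figures.** Section 8.2.2.3 gives differences in AE rate detectable with 80% power, with no reference to grade. A one-sample exact binomial test for an increase reproduces them. It rejects at c or more events, and power = P(X ≥ c) with X ~ Bin(n, p0 + d).

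| n | p0 | d | c | Power |
|---|---|---|---|---|
| 72 | 0.01 | 0.0485 | 3 | 0.800 |
| 72 | 0.85 | 0.1068 | 68 | 0.800 |
| 82 | 0.01 | 0.0415 | 3 | 0.800 |
| 82 | 0.85 | 0.1021 | 77 | 0.800 |
| 312 | 0.01 | 0.0189 | 7 | 0.799 |
| 312 | 0.85 | 0.0534 | 278 | 0.801 |

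The match uses an upper tail of 0.05 at rate 0.01 and 0.025 at rate 0.85. The figures are sound for what they cover; the gap is in what is counted.

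**3. Effect of a shift in grade.** Inputs: 254 qHPV subjects enrolled and 200 planned for 9vHPV (Section 8.1), and the plan's own rate of 0.85. The Grade 3+ counts are assumptions.

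- qHPV: 0.85 × 254 = 215.9, so take 216; 216/254 = 85.0%.
- 9vHPV: 0.85 × 200 = 170; 170/200 = 85.0%.

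The planned percentage is the same in every row below that has cases. The added line uses the Clopper-Pearson 95% interval: lower limit = Beta(0.025; x, n − x + 1), upper limit = Beta(0.975; x + 1, n − x).

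| n | Grade 3+ cases x | x/n | Exact 95% CI |
|---|---|---|---|
| 254 | 0 | 0% | 0 to 1.4% |
| 254 | 6 | 2.4% | 0.9 to 5.1% |
| 254 | 17 | 6.7% | 3.9 to 10.5% |
| 200 | 0 | 0% | 0 to 1.8% |
| 200 | 4 | 2.0% | 0.5 to 5.0% |
| 200 | 13 | 6.5% | 3.5 to 10.9% |

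With four equal strata (assumed; 254/4 ≈ 64 and 200/4 = 50), one case gives 0.04 to 8.4% at n = 64 and 0.05 to 10.6% at n = 50. The cohort is the useful level.

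**4. Are the inputs for a grade line settled?** Three points are not.

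- *Attribution.* Section 8.2.2.3 covers vaccine-associated AEs. Section 9.3.3 collects Grade 3+ events regardless of relatedness, so an AERF count need not be a subset of the planned percentages.
- *Denominator.* Section 8.2.2.3 uses the intention-to-treat (IT) sample, which Section 8.1 describes as seronegative at baseline. Section 7.1 reports safety on every eligible subject with at least one dose. In the planning figures these differ by 353 − 339 = 14 subjects.
- *Source.* Section 9.3.3 wants an AERF for every Grade 3+ clinical toxicity within 14 days. Sections 5.4.7 to 5.4.9 ask for one only when expedited reporting applies, which for Grade 3-4 means serious (monitoring committee) or an unanticipated problem (IRB). The two instructions disagree on exactly the event at issue.

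**The case against.** The strongest reply is that this is a reporting preference. Nothing in Section 8.2.2.3 is miscalculated, no decision rule changes, and nothing stops the investigators from tabulating grades. Grade already drives return to clinic within 24 hours, discontinuation, case reports and the accrual hold. Non-serious AEs also reach the committee in aggregate through the continuation and Protocol Management Team reports (Sections 9.3.2 and 9.3.2.1.1), and a grade layout may sit in appendices that are not shown.

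Much of this stands. A reader might infer that transient Grade 3 reactions go uncounted, or that participants are exposed to unmonitored severe toxicity. The documents support neither inference: the reaction is counted in the any-grade percentage, and individual cases are acted on. The illustration is no evidence that a shift is likely. The any-grade figure stays fixed because its total was held fixed, and the two qHPV intervals overlap.

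What does not stand is that these routes supply the missing result. Reports to a committee are not the stated analysis of a primary endpoint, and the committee list in Section 9.2 has no grade category either. A later severity table would be a choice the plan did not commit to.

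It is also tempting to test the new line against the 2.2% severe injection-site rate in Section 2.4.2. The documents do not give that figure's severity definition, age and sex mix or follow-up window, so it can serve only as context.

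**Conclusion.** The point holds as a limited gap in the planned summary. Severity is graded, and increased severity is a risk the protocol names, but the stated safety results do not show a rise in transient, non-serious Grade 3 reactions except through discontinuation, and not at all after Dose 3. Data capture in principle, participant protection, power, alpha and sample size are not in question.

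Under the assumed counts, two cohorts that differ by 6.7% − 2.4% = 4.3 percentage points in Grade 3+ reactions would report the same 85.0%. With no cases, the added line would still bound the rate at 1.4% (n = 254) or 1.8% (n = 200). These figures treat all 254 and 200 subjects as dosed and assessed. The conclusion rests on the body text; Appendices 14, 19 and 20 could show that grade fields already exist, but would not by themselves put a grade summary into Section 8.2.2.3. The change is worth making because it is inexpensive and widens what the trial can say about tolerability.

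**What to change.** In Section 8.2.2.3 add, descriptively, by vaccine cohort, by dose and across doses:

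- The percentage of subjects with a Grade 3+ injection-site AE and, separately, a Grade 3+ systemic AE, within 7 days (9vHPV) or 14 days (qHPV) of a dose, each with an exact 95% CI.
- The same vaccine-associated definition as the any-grade lines, so that Grade 3+ is a subset of them, with the regardless-of-relatedness count alongside.
- All eligible subjects with at least one dose (Section 7.1) as the denominator, stated explicitly because the adjacent lines use the IT sample.

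Take grades from the Vaccine Report Card and the AERFs required by Section 9.3.3. State that the Section 9.3.3 rule prevails over the expedited-only wording in Sections 5.4.7 to 5.4.9. Add no hypothesis test.

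Cost: a few extra tables and one clarifying sentence. If sites have followed the narrower visit wording, some Grade 3 events may have to be recovered from the Report Cards, so check Appendices 14, 19 and 20 for grade fields first. Downsides: wide intervals within strata and no matched reference rate.

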1.0 OBJECTIVES AND HYPOTHESES

Aim 1:

Using a cross-sectional survey approach, estimate the prevalence of HPV vaccine non-initiation

- a. Examine sociodemographic, behavioral, and medical determinants of HPV vaccine non-initiation

Hypothesis 1: The HPV vaccine initiation rates for cancer survivors will be less than 40% (estimated rate in the general population); subgroups of cancer survivors with particularly low vaccine initiation rates will be identified.

Among cancer survivors identified to be non-immunized in Aim 1, and among additional non-immunized cancer survivors meeting study eligibility criteria:

Aim 2:

Using a single-arm, phase II, open-label, prospective longitudinal trial design, to evaluate the 3-dose qHPV (for patients enrolled on or before 3-1-16) or 9vHPV (for patients enrolled after 3-1-16) vaccine series and measure the following endpoints:

- a. Determine immunogenicity following the third and final vaccine dose
- b. Identify clinical/host factors influencing immunogenicity
- c. Determine the safety/tolerability of the qHPV and 9vHPV vaccine in cancer survivors

Hypothesis 2: Immunogenicity to the qHPV and 9vHPV vaccines will be heterogeneous among cancer survivors, with subpopulations that received the most intense therapy demonstrating inferior immunogenicity. The qHPV and 9vHPV vaccines will be safe and well-tolerated by cancer survivors.

Exploratory sub-aim:

Evaluate the persistence of antibody response at 2 years post vaccine initiation and identify clinical/host factors influencing response persistence.

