2.4.2. Safety: qHPV vaccine: The qHPV vaccine has been safe and well-tolerated in 5 clinical trials enrolling 21,480 subjects⁷³ and in post-licensure safety monitoring.⁷⁴ The most common adverse reactions were headache (vaccine, 28.2%; placebo 28.4%); fever (13.0% vs. 11.2%), and nausea (6.7% vs. 6.5%). The rates of serious adverse events (AEs) were comparable between vaccine and placebo groups²⁸ and occurred at 50% the rate reported for licensed vaccines. Severe injection site reactions were slightly higher in the vaccine group (2.2%) compared to placebo (0.9%).^{73,74} In post-licensure monitoring, AEs were consistent with pre-licensure data with the exception of disproportional reporting (per 100,000 doses of qHPV vaccine distributed) of syncope (8.2/100,000) and venous thromboembolic events (VTE) (0.2/100,000); 94% of syncopal episodes were classified as non-serious and 90% of patients with VTE had a known risk factor.⁷⁴ **9vHPV vaccine:** In clinical trials involving 20,334 immunocompetent males and females between 9 and 26 years of age, the 9vHPV vaccine has been shown to be safe and generally well tolerated compared to the qHPV vaccine. Females age 16-26 who received 9vHPV were more likely to report mild to moderate injection site adverse events compared to those who received qHPV (90.7% vs. 84.9%), with the most common events being pain, swelling, erythema, and pruritis. Adverse event reports in males were lower than in females and were similar to qHPV. There was no increase in reported serious adverse events for 9vHPV compared to qHPV.^{36,69}

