2.10.2 Gaps in Scientific Knowledge to be Addressed: The study will address the following important gaps in scientific knowledge relevant to health promotion and disease prevention among young cancer survivors: (1) prevalence and determinants of HPV vaccine initiation among cancer survivors; (2) adequacy of the 3-dose qHPV and the 3-dose 9vHPV vaccine series in inducing immunogenicity in individuals treated for cancer; (3) impact of humoral immune competence and therapeutic exposures on qHPV and 9vHPV vaccine immunogenicity; and (4) safety and tolerability of the qHPV and 9vHPV vaccines among cancer survivors. If the rates of HPV vaccine initiation are low among cancer survivors, and qHPV and 9vHPV vaccines are immunogenic, safe, and tolerable in cancer survivors, then, this study would provide strong rationale for developing intervention programs to improve HPV vaccine uptake in cancer survivors. Importantly, this research will inform development of these interventions, since we will determine facilitators and barriers in cancer survivors and identify subgroups of survivors at particularly high risk for poor vaccine uptake (and therefore likely to derive the most benefit from targeted interventions). Additionally, this research will inform recommendations for HPV vaccination of this vulnerable population. We will also identify clinical factors associated with inadequate immunogenic response to the vaccine, and the impact of humoral competence on this response, providing a foundation for future development of alternative vaccination strategies (e.g., alterations in timing, dose and/or schedule) in any subgroups that are unable to mount an adequate response to the standard 3-dose vaccine series. Given the large and ever-increasing number of young cancer survivors in the U.S., this research could potentially result in substantial benefits to this vulnerable population, including primary prevention of HPV-related malignancies and their associated morbidity and mortality. Additionally, this study will form the basis for future investigations aimed at determining the efficacy of the 9vHPV vaccine in reducing HPV-related morbidity in this population.

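### Safety inference in 8.2.2.3 rests on tests of difference with no confidence intervals, so the planned analysis cannot by itself support the safety part of Hypothesis 2

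*Combined protocol and SAP*

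**What the plan says.** Section 1.0, Hypothesis 2, states: "The qHPV and 9vHPV vaccines will be safe and well-tolerated by cancer survivors". Section 7.2 lists safety/tolerability among the primary endpoints of Aim 2. Section 2.10.2 ties the case for programmes to raise uptake partly to a finding that the "qHPV and 9vHPV vaccines are immunogenic, safe, and tolerable in cancer survivors".

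Section 8.2.2.3 compares the percentages of subjects with injection-site, systemic and serious AEs with rates reported for a general population matched on age and sex. The method is: "Chi-square and exact tests will be used for comparison depending on the rarity of events". The section also plans frequencies and percentages by type, by dose and across doses, and the percentage who stop vaccine because of an AE. On power it says "Our smallest PP subsample of 72 young females will provide 80% power to detect a difference of 0.0485 in AE rates if true rate=0.01", with further figures for samples of 82 and 312, and "Type I error=.05 is assumed for each comparison". Neither 8.2.2.3 nor 9.2 mentions a confidence interval or limit for an AE rate.

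Immunogenicity is treated differently. In 8.2.2.1 and 8.2.2.4, titres and seropositivity are judged by confidence limits, including outcomes labelled exploratory.

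**The concern.** The safety part of Hypothesis 2 claims that there is no important excess of AEs. A test of no difference is built to detect an excess. When it fails to reject, the cause may be that there is no excess or that there is too little information, and the p-value does not separate the two. The smaller the sample and the rarer the event, the more likely a non-significant result becomes, whatever the truth.

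At stake is what the trial can say to those who would recommend vaccination for survivors. Section 9.1 describes the safety profile in this group as unknown. A table of percentages and p-values would not state how large an excess remains compatible with the data.

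**Working it through.** **Inputs.** Alpha is 0.05 per comparison (8.2.2.3; sidedness not stated). Cohort sizes are 254 for qHPV and 200 for 9vHPV (8.1). The smallest stratum is 72 and the stated total is 312 (8.2.2.3). The illustrative reference rate is 2.2%, so a doubling is 4.4% (2.4.2).

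**Step 1: reproduce the plan's figures.** Model: X ~ Binomial(n, p), tested against a fixed rate p0. The two-sided exact p-value sums the probabilities of all outcomes no more likely under p0 than the one observed (the minimum-likelihood test). Power is P(X ≥ c | p0 + difference), where c is the smallest high count that rejects.

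| n | p0 | c | stated difference | power |
|---|---|---|---|---|
| 72 | 0.01 | 3 | 0.0485 | 0.800 |
| 72 | 0.85 | 68 | 0.1068 | 0.800 |
| 82 | 0.01 | 3 | 0.0415 | 0.800 |
| 82 | 0.85 | 77 | 0.1021 | 0.800 |
| 312 | 0.01 | 7 | 0.0189 | 0.799 |
| 312 | 0.85 | 278 | 0.0534 | 0.801 |

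All six reproduce. At a 1% rate, 80% power requires a rise to 0.01 + 0.0485 = 5.85% with 72 subjects (5.9-fold), or to 0.01 + 0.0189 = 2.89% with 312 (2.9-fold).

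**Step 2: chance of missing a doubling from 2.2% to 4.4%.** Miss = P(X ≤ c − 1 | n, 0.044). The equal-tailed exact test, which requires P(X ≥ c | 0.022) ≤ 0.025, is shown beside it as a sensitivity check. It does not reproduce all the figures in Step 1.

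| n | c, minimum-likelihood | miss | c, equal-tailed | miss |
|---|---|---|---|---|
| 254 | 11 | 44% | 12 | 56% |
| 200 | 9 | 48% | 10 | 61% |
| 72 | 5 | 79% | 5 | 79% |
| 312 | 13 | 38% | 13 | 38% |

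Section 8.2.2.3 names the intention-to-treat sample. With the 96% seronegative share assumed in 8.1, the cohorts become 0.96 × 254 ≈ 244 and 0.96 × 200 = 192. The miss rates are then 49%, and 53% to 66%.

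**Step 3: what a non-significant result leaves open.** The exact (Clopper-Pearson) limits for x events in n are the 0.025 quantile of Beta(x, n − x + 1) and the 0.975 quantile of Beta(x + 1, n − x).

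- 8/200 = 4.0%: minimum-likelihood p = 0.088; interval 1.7% to 7.7%. Against a fixed 2.2%, the difference is 4.0 − 2.2 = 1.8 points, with interval 1.7 − 2.2 = −0.5 to 7.7 − 2.2 = 5.5 points. The upper limit is 7.7/2.2 = 3.5 times the reference.
- 10/254 = 3.9%: p = 0.080; interval 1.9% to 7.1%, so the upper limit is 7.1/2.2 = 3.2 times the reference.

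Both are the largest non-significant counts at their sample size under the test that matches the plan.

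**The case against.** The strongest reply has four parts.

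- **Safety is not assessed by tests alone.** Percentages by type and dose and the discontinuation rate are planned. There is also committee reporting (9.2), reporting of Grade 3 or higher toxicities (9.3.3) and an accrual hold (9.4). This stands, and a reader with the counts could compute the intervals. But the monitoring provisions are not an analysis of Hypothesis 2, and the tests remain the only inferential method.
- **The plan never says p > 0.05 will be read as safe.** A reader might infer that rule from Hypothesis 2 and the tests together, but no passage states it. What the documents show is a hypothesis for which the planned inference supplies no adequate support.
- **The illustration is not a planned comparison.** Severe injection-site reaction is not among the three listed categories, and 2.2% is neither age- and sex-matched nor a 9vHPV figure. All true, so it is an assumption. It is also tempting to say that a doubling is missed half the time or more. That does not hold in general: under the matching test the miss rate is 44% at 254, 48% at 200 and 38% at 312, and 22% if both cohorts (254 + 200 = 454) were pooled. Pooling is not stated, and the AE windows differ (7 versus 14 days). The plan also discloses its detectable differences, including smaller relative ones for common events: "a difference of 0.1068 if the true rate=0.85" at n=72.
- **Intervals do not cure low power.** Correct. If the true rate is 2.2%, the upper 95% limit falls below 4.4% with probability only 34% at n=254 and 36% at n=200. The intervals make that limitation visible.

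**Conclusion.** The point holds in a limited form. The inferential safety analysis consists of tests of difference, no interval is planned, and a non-significant result would not rule out an important excess. The planned analysis therefore cannot by itself support the safety part of Hypothesis 2. The stated detectable differences are correct, and nothing here suggests that the vaccines are unsafe.

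The size of the problem depends on sample size and test. For a doubling of 2.2%, the miss rate is 44-56% in the qHPV cohort and 48-61% in the 9vHPV cohort; the lower figures come from the test that reproduces the plan's numbers. It is 79% in a stratum of 72. These figures assume analysis by cohort, the full cohort sizes, and a reference rate known without error; allowing for its sampling error would lower power. The logical point does not depend on the 2.2%.

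**What to change.** In 8.2.2.3, for each AE category, by dose and across doses and by vaccine cohort, report:

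- the survivor percentage with an exact 95% confidence interval;
- its difference from the reference rate with a 95% confidence interval, stating whether the reference is treated as fixed.

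Word the Hypothesis 2 safety conclusion by the upper limits, that is, the largest excess the data do not rule out. State that a non-significant test is not evidence of comparable safety. Keep the chi-square and exact tests as secondary.

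The cost is SAP wording and extra table columns, with no new data or subjects. The downside is a more cautious safety statement for rare events, where the upper limits will be wide.
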